7. OUTLINE OF STUDY VISITS

Baseline Visit (SA 1 and 2, Table 1). After informed consent, eligible participants will be scheduled to arrive for an overnight visit in the DCRU/CRU within a standardized time interval (< 2 weeks) from informed consent. During the evening, participants will undergo questionnaire administration, blood pressure measurements, application of the MultiSense™ monitoring device, and anthropometry. They will be provided dinner and undergo polysomnography (PSG). In the morning, participants will undergo fasting venipuncture, overnight urine collection, ECHO, 6 minute walk test and blood pressure measurements. For those with PAF (cases), hook-up for continuous ECG monitoring will be performed along with education regarding how to handle the device and bathing instructions, etc. All measurements in the DCRU/CRU will be performed blinded to PAF status. The only unblinded staff will be a dedicated research assistant who will perform the ECG monitoring hook-up. Blinded staff will collect and process data and perform data entry. After the baseline visit, participants with PAF (n=150) will undergo hook-up of the ECG monitor and an activity monitor at the baseline visit to wear for a 7-21 day period. The monitors will be picked up by a courier service. If eligible for the 7T MRI sub-study (cases - AHI \geq 15 and agree to CPAP treatment, controls AHI \geq 15), they will be consented and all questions answered. The individuals who serve as controls who are identified to have sleep apnea (AHI \geq 5) or for those with PAF who have an AHI ranging from 5-15 on the baseline sleep study in the Clinical Research Unit will be notified of these results and the physician will be contacted if the participant provides permission.

Table 1. Timeline of Events for SA 1 and 2	
EVENING	
5PM	DCRU/CRU Arrival/Intake
515PM	Questionnaire Administration
600PM	Anthropometry
630PM	Dinner
9PM	PSG Hook-Up
10PM	Blood Pressure Measurements in Triplicate
1030PM	Lights Out-Overnight PSG
7AM	Lights On/Blood Pressure Measurements in Triplicate
715AM	Fasting Venipuncture
745AM	Overnight Urine Collection
8AM	Echocardiography
830AM	Breakfast
9AM	Continuous ECG monitoring hook-up and education for cases with PAF
930AM	DCRU/CRU Discharge

[figure not shown]
Follow-Up Visit (SA3). Those with SDB (AHI $>$ 15) without evidence of central apnea (central apnea index $>$ 5) or Cheyne Stokes Respirations via baseline visit PSG and who have PAF will undergo the following:

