2) POLYSOMNOGRAPHY (PSG). *Procedure for PSG*: Research PSG will be performed using the Compumedics E-series system (Abbott'sford, AU) which will include 3 cortical encephalograms, bilateral electro-oculograms, a bipolar submental electromyogram, thoracic and abdominal respiratory inductance plethysmography, airflow (by nasal-oral thermocouple and nasal cannula pressure recording), oximetry (using highly sensitive finger pulse oximeter, sampling frequency 25Hz), electrocardiogram (ECG) at 250Hz (used to derive HRV measures of autonomic function); body position (mercury switch sensor), bilateral leg movements. EEGs are recorded at 125Hz. Sensors will be calibrated, and signal quality/impedance checked by a certified technician, using standardized techniques. PSG scoring criteria are documented in the Case Sleep Research Manual of Procedures (**Appendix B**). ***Relevant PSG Variables***: Apneas will be classified as "central" or "obstructive" according to the absence or presence of respiratory effort respectively. Hypopneas will be scored as a 50% amplitude reduction in inductance or flow and associated 3% oxygen desaturation or arousal. Periodic breathing will be defined as airflow or inductance channels increasing and decreasing at least 50% from the maximum, in a cyclic waxing and waning or "sinusoidal" manner for a consecutive period of ≥ 10 min.

Procedure for PSG ECG Signal Extraction: ECG monitoring data from the PSG Baseline and Follow Up Exams will be processed and analyzed by the Case Electrophysiology Core (Director: [name], Nord Professor of Engineering). Data will be exported as European Data Format (EDF) ECG files into customized Matlab programs that

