c) The *Sleep Habits and Medical Condition Questionnaire*¹⁰¹, which includes comorbidities, medication use (including anti-arrhythmic medications), caffeine use, smoking, alcohol use, etc., d) The *Medical Outcomes Survey-SF 36 (MOS-SF)*¹⁰², a standardized tool for assessing general health status, physical and social functioning, and fatigue, e) *Patient Health Questionnaire-9 (PHQ-9)*, which assesses depression symptoms. It has ten questions where the answers will be added to indicate severity of depression. The Research Assistant will score depression questionnaires and if the score is indicative of depression (10 or greater) the Research Assistant will then contact a study physician who will determine appropriate referrals and responses and contact the participant to advise him to seek medical/psychiatric consultation. If there was any indication that a participant was in imminent danger to himself or others, the participant would be advised to go to the nearest emergency room for evaluation by a psychiatrist. If signs of depression, anxiety or other psychological disorders were evident without evidence for immediate risk, the participant would be advised to contact a psychologist for further evaluation. f) *Daily ECG/Activity Log*, which will be completed during 7-21 day ECG monitoring including data on sleep/wake times including naps, periods of vigorous activity, caffeine use, alcohol use, smoking, monitor removal time and symptoms (e.g. palpitations, dyspnea, chest pain) g) *Atrial Fibrillation Effect on Quality-of-life*, a 20-item questionnaire that assesses the impact of atrial fibrillation on quality of life.

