10. DATA ANALYSIS

EXPOSURES: *Primary:* 1) SDB defined by AHI, i.e. number of apneas + hypopneas/hour of sleep. *Secondary:* 1) Hypoxia: % sleep time with $\text{SaO}_2 < 90\%$, 2) Obstructive Sleep Apnea [obstructive apneas and hypopneas/hour of sleep, obstructive apnea hypopnea index (OAHI)], 3) Central Sleep Apnea [central apneas/hour of sleep, Central Apnea Index (CAI)], 4) Periodic Breathing and 5) EEG arousals [per hour of sleep, Arousal Index (AI)].

OUTCOME: 1) PAF (SA1) and 2) AF burden defined as frequency of AF paroxysms overall and based on self-reported sleep vs. wake (SA2 and 3)

COVARIATES: Age, race, body mass index (BMI, kg/m^2), waist circumference (cm), anti-arrhythmic/beta blocker/calcium channel blocker/ACE inhibitor/angiotensin receptor blocker medications, pacemaker, defibrillator, heart failure (NYHA class), BP, diabetes mellitus, left atrial volume, LVEF, caffeine use, alcohol use and smoking (current versus never smoker or pack years) and activity level. When assessing hypoxia as the relevant exposure, pulmonary disorders will be included as potential confounders.

Table 2. Mediator (SA1) or Outcome (SA3)

Domain	Primary	Secondary	Rationale
Echocardiographic Measures	Left Atrial Volume (ml/m^2)	LA Pressure, LA Systolic Strain, RA area, RA Pressure, LAA Peak Anterograde Flow Velocity (cm/s), Right Atrial Pressure (mmHg), LVEF, LVMI, LVH (concentric LVMI >0.41 , eccentric ≤ 0.41).	Left Atrial Volume predicts risk of AF and PAF ¹⁰³⁻¹⁰⁶ . Secondary measures also associated with AF.
Autonomic Function (Heart Rate Variability)	SDNN (ms) (Time Domain HRV Measure)	Time Domain (r-MSSD (ms), pNN50), Frequency Domain [LF (Hz), HF (Hz), LF/HF], Graphical Parameters (HR patterns, power spectral analysis, Poincaré plots and beat-by-beat HR tachograms) and Novel non-linear measures (e.g. Conditional Entropy ¹⁰⁷).	Reduced SDNN and LF/HF have been identified as AF triggers ⁴⁰ .
Systemic Inflammation	hs-CRP (mg/L)	IL-6 (pg/ml), sIL-6R (ng/mL)	hs-CRP and IL-6 associated with SDB and AF ⁴⁷⁻⁴⁹ . s-IL6R varies with overnight hypoxia ⁴⁶
Oxidative Stress	Endothelin-1 (pg/ml)	Urinary isoprostane 8-epi-prostaglandin F2a (ng/ mmolCr), Oxidized LDL (U/L)	Endothelin-1 implicated in AF ⁵⁷⁻⁵⁹ . Isoprostane ⁶⁰⁻⁶² and oxidized LDL sensitive to SDB ⁷⁶ .

ANALYTIC METHOD BY AIM.

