SA 1. Quantify the extent that SDB and its subtypes are associated with PAF. This aim will be addressed by fitting conditional logistic regression models that condition on the matched pair. We will separately analyze each SDB variable (primary variable: AHI) to obtain an estimate and 95% CI of the odds ratio of PAF for a 1-unit increase in the SDB exposure. Non-linear effects between SDB and the log odds of PAF will be assessed using restricted cubic splines. Knots for the spline will be based on the SDB threshold at which PAF risk increases. Unadjusted and hierarchical adjusted models will be performed using the covariates listed above.

The secondary exposure variables (e.g. hypoxia, OAHI, CAI, AI) will be considered in separate models.

Exploratory Aim 1a. Cardiac structure, autonomic and biochemical variables (Table 2) will explain a proportion of the SDB and PAF relationship. This aim will be addressed by applying Pearl's mediation formula ¹⁰⁸ to the conditional logistical regression model. This approach will allow a causally sound definition of the mediation effect of a given intermediate variable in the relationship between SDB (defined by AHI) and PAF. The approach involves a model for each mediator (e.g. a general linear model for a continuous mediator) and possibly a random effect to account for clustering due to matching and can be thought of as a generalized structural equations model. This approach will allow us to simultaneously assess multiple mediators and will also allow us to consider AHI as a continuous variable. Each model will be fit using likelihood methods and model fit will be checked using appropriate information criteria. After fitting the overall model, we will obtain, for each mediator, an estimate of the indirect effect (e.g. the portion of the overall effect of SDB on PAF mediated through the intermediate variable). A bootstrap resampling technique will be used to obtain a 95% CI for each indirect effect. If the CI does not contain zero, this will indicate statistically significant mediation.

Exploratory Aim 1b. Explore age interactions in the SDB-PAF relationship. Each conditional logistic regression model will include an interaction between age and SDB to investigate if age is a modifier of the effect of SDB on PAF, i.e. whether the odds ratio of PAF for a 1-unit increase in SDB varies by age.

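### The SA1 covariate list includes anti-arrhythmic drugs, which cases may take because of PAF; the main SA1 adjusted model should leave them out and show them in a sensitivity analysis

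*Combined protocol and SAP*

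**What the plan says.** Sections 9 and 10 carry the same covariate list, not tied to any one aim. It includes "anti-arrhythmic/beta blocker/calcium channel blocker/ACE inhibitor/angiotensin receptor blocker medications" as a single slash-joined item. The SA1 paragraph then applies the list to conditional logistic models of PAF case versus control: "Unadjusted and hierarchical adjusted models will be performed using the covariates listed above".

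Four other places bear on what the anti-arrhythmic term means in SA1:

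- Section 6 (Recruitment Overview) says that clinical care of PAF may include anti-arrhythmic drugs. It limits the approach to patients whose PAF was diagnosed in the last 6 months and who have not had ablation.
- Section 7 (Baseline Visit) places drug-use recording at the study visit: "During the evening, participants will undergo questionnaire administration, blood pressure measurements". Section 8 (Questionnaires) describes the instrument, "which includes comorbidities, medication use (including anti-arrhythmic medications), caffeine use, smoking, alcohol use, etc".
- Section 5, case exclusion 20, removes users of rate-controlling anti-arrhythmics (Classes I-III and V) only if PAF has not recurred. Treated cases with continuing PAF can enrol.
- Section 5 (Controls) applies the case exclusions to controls, who by definition have no AF.

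**The concern.** In SA1 the outcome is PAF. A drug given for PAF and recorded after diagnosis may be a consequence of that outcome rather than a confounder of the AHI-PAF association. A model with the term compares cases and controls at equal treatment status, which is not the comparison SA1 sets out to make.

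The likely direct cost is precision. If many cases and few controls are users, the drug term separates cases from controls by itself, and drug-discordant pairs then say little about AHI. Exclusion 20 could make this worse. Controls have no PAF to recur, so read literally it removes every control on those classes. The plan may not intend that reading, but it does not say otherwise.

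The adjusted odds ratio matters because the study is meant to show an association independent of confounders. Matching alone covers only age, gender, race and BMI.

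**Working it through.** **Inputs.** From section 10, Power by Aim, SA1: 300 participants (150 pairs), two-sided alpha 0.05, odds ratio 1.50 per SD of AHI, zero AHI correlation between cases and controls, probability of PAF 0.20 at mean AHI. The documents give no drug-use rates and no link between drug use and AHI. Both are assumed below.

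**1. The plan's own figure.** For logistic regression on one continuous covariate, n = (z_alpha + z_beta)^2 / [P(1-P)(ln OR)^2].
- OR 1.50, 80% power: (1.960 + 0.842)^2 / (0.16 x 0.1644) = 7.849 / 0.02630 = 298.4.
- OR 1.60, 90% power: (1.960 + 1.282)^2 / (0.16 x 0.2209) = 10.507 / 0.03534 = 297.3.

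Both agree with the stated 300.

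**2. Benchmark for 1:1 pairs without the drug term.** With zero correlation the within-pair AHI difference has variance 2, so near the null the information on ln OR is 150 x 2 / 4 = 75. Then z = sqrt(75 x 0.1644) - 1.960 = 3.511 - 1.960 = 1.55, or power of about 94%. Simulation gives about 93%. This exceeds 80% because the plan's formula uses P = 0.20 and the design has one control per case.

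**3. Adding a yes/no drug term, use unrelated to AHI.** Simulation: 6,000 studies of 150 pairs per scenario, control AHI N(0,1), case AHI N(ln 1.50, 1), conditional logistic regression fitted on within-pair differences, Wald test.

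| Assumed use, cases v controls | SE multiplier | Power |
|---|---|---|
| Term not in model | 1.00 | about 93% |
| 20% v 5% | 1.06 | 90% |
| 40% v 20% | 1.05 | 90% |
| 40% v 5% | 0.150/0.125 = 1.20 | 81-82% |
| 20% v 0% | - | 87% |
| 40% v 0% | - | 74% |
| One combined term for all five classes, 70% v 50% | 1.05 | 91-92% |

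The estimate stays centred near 1.50 here; only precision is lost. At 40% v 5% the expected pairs are 150 x 0.40 x 0.95 = 57 with only the case treated, 150 x 0.60 x 0.05 = 4.5 with only the control treated, and 88.5 concordant.

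**4. No control users.** Every discordant pair then has a treated case. The drug coefficient has no finite estimate, and those pairs drop out of the AHI odds ratio. At 40% case use, 150 x 0.60 = 90 pairs remain: information 90 x 2 / 4 = 45, z = sqrt(45 x 0.1644) - 1.960 = 0.76, power about 78% by approximation and 74% by simulation. At 30%, 50% and 70% case use, 105, 75 and 45 pairs remain and simulated power is 81%, 66% and 41%. The chance of separation at 40% case use is (1 - 0.60 x p0)^150, where p0 is control use: 41% at p0 = 1%, 16% at 2%, 1% at 5%.

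**5. When bias would arise, and in which model.** Illustrations at 40% v 5%:
- *Prescribing among cases depends on AHI.* At a log-odds slope of +0.5 or -0.5 per SD, the model with the term gives an odds ratio of 1.32 or 1.75 when the truth is 1.50, and rejects a true null 16-17% of the time. At slopes of +/-0.25 it rejects about 7%.
- *The drug itself shifts AHI.* At +0.5 or -0.5 SD with a true odds ratio of 1.0, the model without the term gives 1.19 or 0.84 and rejects 30-31%. With the term it gives 1.00 and rejects 4-5%.

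The first mechanism leaves an AHI difference of 0.47 SD between treated and untreated cases, the second 0.50 SD. With 60 treated and 90 untreated cases the 95% CI half-width is 0.33 SD, so the data would not tell them apart.

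**The case against.** Several objections have force.

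- **The unadjusted matched odds ratio is planned.** It does not contain the term. This stands and limits the concern to the adjusted steps.
- **A reader might infer that the adjusted result rests on an unplanned choice.** That goes too far. A series of hierarchical models is planned, with no data-driven covariate selection rule for SA1. The unstated order of entry is missing detail; the substantive problem is that the list contains treatment for the outcome.
- **A reader might infer that the adjusted odds ratio will be biased.** The documents give neither drug rates nor any drug-AHI link. If the five classes enter as one combined term, the effect is small: at 70% v 50% and a slope of +/-0.5, null rejection is about 6%.
- **A reader might infer that the study becomes underpowered.** At odds ratio 1.50, every step 3 scenario with some control users stays above the stated 80%. Of the no-control-user scenarios, 20% and 30% case use also stay above it; 40% and higher fall below.
- **Omitting the term can also be wrong.** AHI, too, is measured after diagnosis. At 40% v 5%, wrongly omitting the term has the larger null-rejection error of the two illustrations (30-31% against 16-17%). So the data cannot justify omission. Its basis is that the term can be a consequence of case status, and both results must be shown.

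**Conclusion.** The point holds as a fault in the adjustment rule: the SA1 covariate list contains a treatment for the SA1 outcome, recorded after diagnosis. That much needs no assumption. The size does. Precision is lost if case use exceeds control use: from negligible at 20% v 5%, to about 81% power at 40% v 5%, to about 74% at 40% v 0%, against about 93% without the term. Separation is a practical risk if exclusion 20 is applied literally to controls. Bias in either model is possible but not shown, and its direction cannot be settled from the study's own data. Confidence is high that the drugs are listed and that precision falls if use is unequal, and low on the size of any bias. It should be corrected before analysis.

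**What to change.** Amend the SA1 text of the analysis plan:

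1. Code anti-arrhythmics separately from the other four drug classes and define which drugs count. Exclusion 20 and the covariate list are not mapped to each other.
2. Leave anti-arrhythmics out of the main SA1 adjusted model.
3. Report the same model with anti-arrhythmics added, labelled as a sensitivity analysis. Give the number of drug-discordant pairs, and use a Firth-penalised or exact conditional fit if there is separation.
4. Present the two results together, without claiming that the data show which is right.

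The cost is a few sentences and one extra model; data collection and sample size do not change. The downside is that use of these drugs for disease that preceded AF, or any effect of the drugs on AHI, is handled only in the sensitivity model.

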- 1) Left and Right Atrial Parameters: Left atrial volume by using the biplane area-length method ⁷⁹, right atrial area (from the 4-chamber view), left atrial pressure estimated from the ratio of early diastolic transmural flow velocity to early annular tissue velocity ⁸¹ and right atrial pressure based on the diameter of the inferior vena cava and its response to a "sniff" will be assessed ⁸². Peak left atrial systolic strain, a measure of LA remodeling which is inversely related to fibrosis in PAF ⁸³, will also be measured.
- 2) Left Atrial Appendage (LAA) Parameters: LAA wall motion velocity, a measure associated with AF will be assessed ⁸⁴. A value of >40 cm/s, has been noted to be an independent predictor of NSR maintenance in AF⁴⁴. LAA tissue velocity, a more readily obtained and sensitive LAA dysfunction measure will also be measured ⁸⁴.
- 3) Left ventricular ejection fraction (LVEF, %): This will be derived from left ventricular end-diastolic volume (LVEDV) and end-systolic volume (LVESV): $[(\text{LVEDV} - \text{LVESV}) / \text{LVEDV} \times 100]$ ⁸⁵.
- 4) Left ventricular mass index (LVMI): This will be calculated by a validated formula ⁸⁶ : $\text{LVMI} = \{0.8 \times [1.04 \times (\text{LVIDd} + \text{IVST} \times \text{LVPWT})^3 - (\text{LVIDd})^3] + 0.6\} / \text{height}^{2.7}$, where LVIDd is LV internal diastolic diameter, IVST is interventricular septal thickness and LVPWT is LV posterior wall thickness, measured in centimeters.
- 5) Left ventricular hypertrophy (LVH): Using previously published thresholds, we will define LVH as an LVMI of 49.2 g/m^{2.7} for men and 46.7 g/m^{2.7} for women ⁸⁷. Subjects with LVH will be classified as having concentric hypertrophy if relative wall thickness $[(\text{LVPWT} \times \text{IVST}) / \text{LVIDd}]$ is >0.41 or eccentric hypertrophy if ≤ 0.41 ⁸⁸.

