9. ANALYTIC PLAN

EXPOSURES: **Primary:** 1) SDB defined by AHI, i.e. number of apneas + hypopneas/hour of sleep. **Secondary:** 1) Hypoxia: % sleep time with $\text{SaO}_2 < 90\%$, 2) Obstructive Sleep Apnea [obstructive apneas and hypopneas/hour of sleep, obstructive apnea hypopnea index (OAH)], 3) Central Sleep Apnea [central apneas/hour of sleep, Central Apnea Index (CAI)], 4) Periodic Breathing and 5) EEG arousals [per hour of sleep, Arousal Index (AI)].

OUTCOME: 1) PAF (SA1) and 2) AF burden defined as frequency of AF paroxysms overall and based on self-reported sleep vs. wake (SA2 and 3)

COVARIATES: Age, race, body mass index (BMI, kg/m^2), waist circumference (cm), anti-arrhythmic/beta blocker/calcium channel blocker/ACE inhibitor/angiotensin receptor blocker medications, pacemaker, defibrillator, heart failure (NYHA class), BP, diabetes mellitus, left atrial volume, LVEF, caffeine use, alcohol use and smoking (current versus never smoker or pack years) and activity level. When assessing hypoxia as the relevant exposure, pulmonary disorders will be included as potential confounders.

Table 2. Mediator (SA1) or Outcome (SA3)

Domain	Primary	Secondary	Rationale
Echocardiographic Measures	Left Atrial Volume (ml/m^2)	LA Pressure, LA Systolic Strain, RA area, RA Pressure, LAA Peak Anterograde Flow Velocity (cm/s), Right Atrial Pressure (mmHg), LVEF, LVMI, LVH (concentric $\text{LVMI} > 0.41$, eccentric ≤ 0.41).	Left Atrial Volume predicts risk of AF and PAF ¹⁰³⁻¹⁰⁶ . Secondary measures also associated with AF.
Autonomic Function (Heart Rate Variability)	SDNN (ms) (Time Domain HRV Measure)	Time Domain (r-MSSD (ms), pNN50), Frequency Domain [LF (Hz), HF (Hz), LF/HF]], Graphical Parameters (HR patterns, power spectral analysis, Poincaré plots and beat-by-beat HR tachograms) and Novel non-linear measures (e.g. Conditional Entropy ¹⁰⁷).	Reduced SDNN and LF/HF have been identified as AF triggers ⁴⁰ .
Systemic	hs-CRP (mg/L)	IL-6 (pg/ml), sIL-6R (ng/mL)	hs-CRP and IL-6 associated with SDB and AF ⁴⁷⁻⁴⁹ . s-IL6R varies with overnight

Inflammation			hypoxia ⁴⁶
Oxidative Stress	Endothelin-1 (pg/ml)	Urinary isoprostane 8-epi-prostaglandin F2a (ng/mmolCr), Oxidized LDL (U/L)	Endothelin-1 implicated in AF ⁵⁷⁻⁵⁹ . Isoprostane ⁶⁰⁻⁶² and oxidized LDL sensitive to SDB ⁷⁶ .

ANALYTIC METHOD BY AIM.

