SA2. Examine patterns of PAF burden via 7-21 day continuous ECG monitoring relative to SDB. We will model the relationship between mean frequency AF paroxysm variation and SDB (e.g. AHI considered as a continuous variable). A linear regression model will be used to assess possible quadratic and threshold effects of SDB on variation. These models may also include sleep state by SDB interaction terms (along with the state indicator) to examine if the effect of SDB on variation differs by sleep state. Maximum likelihood (based on a normal distribution for variation if appropriate) will be used to fit models, and the Akaike Information Criterion (AIC) will be used to select the best fitting model. Estimates of the effect of SDB on variation (and corresponding 95% CI) will be obtained based on the selected model.

SA3. Examine the effects of SDB (AHI \geq 15) treatment for 3 months on AF paroxysm frequency and also measures of autonomic function, cardiac morphology, biochemical measures in those with SDB and PAF. For this subgroup of SDB (AHI \geq 15) and PAF, we will perform paired t-tests to compare pre- and post-treatment mean outcomes (Primary outcome: AF paroxysm frequency from 1-week ECG monitoring) and also ECHO and biochemical measures. For any outcome for which a departure in normality is found (based on the Shapiro-Wilk test) but a transformation of the outcome cannot be found to adequately address the issue, we will use the Wilcoxon signed rank sum test to detect a difference in the distribution of the pre- and post- responses. This assessment is not intended to be confirmatory, but rather to provide estimates of variability and effect sizes to inform future studies/randomized trials. Linear regression models will then be developed to model PAF burden at the 3 month visit by conditioning on baseline PAF burden, baseline SDB,

and time from baseline to 3 month visit. Additional adjusted models will carefully consider the covariates list above.

POWER BY AIM.

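### Minor internal inconsistency: both copies of Table 2 put the 0.41 concentric/eccentric cut on LVMI, while Section 8 puts it on relative wall thickness

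*Combined protocol and SAP*

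**What the plan says.** Section 8 (Study Procedures and Data Collection), under Relevant ECHO Variables, item 5, works in two steps.

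- LVH is defined from LVMI by sex: "we will define LVH as an LVMI of 49.2 g/m^{2.7} for men and 46.7 g/m^{2.7} for women".
- Those who meet that definition are then divided by another variable: "Subjects with LVH will be classified as having concentric hypertrophy if relative wall thickness" is above 0.41, and as eccentric if it is 0.41 or less.

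Table 2 lists the SA1 mediators and SA3 outcomes. It appears in Section 9 (Analytic Plan) and again in Section 10 (Data Analysis). In both copies LVH stands in the secondary column of the echocardiographic row, with the subtype rule in parentheses. Section 10 prints "LVH (concentric LVMI >0.41", followed by the eccentric class at or below the same value. Section 9 prints "LVH (concentric $\text{LVMI} > 0.41$, eccentric ≤ 0.41". Neither copy mentions relative wall thickness.

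**The concern.** The two places give the same number and the same class names but name different variables. This matters because Table 2 is the list an analyst would work from. Exploratory Aim 1a points to it for the candidate mediators, and its title says that it also supplies the SA3 outcomes.

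If the Table 2 rule were coded as it stands, the LVH subtype would take a single value in everyone with LVH. It could not separate subtypes in the mediation work or register any change in geometry between baseline and the 3-month visit. It would also disagree with the definition given in the procedures section.

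**Working it through.** There is no calculated figure in the plan to reproduce. The check compares two stated rules, using numbers that are all in the documents.

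**Inputs**

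- LVH entry threshold on LVMI: 49.2 g/m^2.7 for men and 46.7 g/m^2.7 for women (Section 8, item 5).
- Subtype cut: 0.41, on relative wall thickness (Section 8, item 5) or on LVMI (Table 2, Sections 9 and 10).
- Reading adopted: LVH means an LVMI at or above the sex-specific threshold. Section 8 gives the value without a direction, but hypertrophy can only mean the upper side.

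**Step 1. Compare the entry threshold with the Table 2 cut.** Both are on the LVMI scale.

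- Men: 49.2 / 0.41 = 120.0
- Women: 46.7 / 0.41 = 113.9

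Anyone classed as having LVH therefore has an LVMI of at least 46.7, far above 0.41. Under Table 2 the concentric condition is always met and the eccentric condition never is. No assumption about the distribution of LVMI is needed.

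**Step 2. Cross-classify participants with LVH under the two rules.**

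| Relative wall thickness | Section 8 | Table 2 | Agree? |
|---|---|---|---|
| above 0.41 | concentric | concentric | yes |
| 0.41 or less | eccentric | concentric | no |

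All the disagreement falls in the second row. The share of LVH participants affected equals the share who are eccentric under Section 8. The documents do not give that share, so it cannot be put as a number.

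**Step 3. Trace where the variable is used.**

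- The primary echocardiographic measure in Table 2 is left atrial volume. LVH is secondary.
- LVH is not in the covariate list of Section 9 or Section 10, so adjustment of the SA1 models does not depend on it.
- The power statements for SA1, Aim 1a, SA2 and SA3 rest on AHI, PAF status, a generic mediated proportion and PAF burden. None uses LVH.
- Of SA3 the plan says: "This assessment is not intended to be confirmatory".

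**The case against.** The strongest reply is that this is a labelling slip and harmless. Section 8 gives a complete working definition: the LVH thresholds by sex, the variable that carries the split, the cut and a citation. Table 2 gives only a parenthetical reminder in a list. A competent analyst would notice that an LVMI of 0.41 is nowhere near the LVH thresholds and would go back to Section 8. No model or test is specified for the subtype by name, and LVMI and LVH are also listed in their own right, so left ventricular mass is analysed whatever the subtype label says.

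Most of this stands, and it is why the point is minor. It does not remove the point. The analysis sections are where a programmer looks first, Aim 1a refers to Table 2 directly, and no sentence gives Section 8 precedence.

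Damage in reading the PDF is an unlikely explanation. LVMI stands next to 0.41 in both copies of the table, although the markup differs between them.

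A reader might go further and infer that the LVMI and relative wall thickness formulas in Section 8 are also wrong, because of the symbols in the text as it reads here. The documents do not support that. Mathematical symbols may have been altered in extraction, the plan says that LVMI follows a validated and cited formula, and the cited sources are not available. The inconsistency in Table 2 does not depend on how those formulas are read.

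**Conclusion.** The point holds as a minor internal inconsistency. Two sections attach one cut to two different variables. Under the Table 2 version the eccentric class is empty by construction, because the LVH thresholds are 113.9 and 120.0 times the cut. The only assumption is that LVH means an LVMI at or above the stated threshold.

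The reach is limited to one secondary echocardiographic variable, in exploratory mediation (Aim 1a) and in the non-confirmatory pre/post comparison (SA3). The primary analyses and the power calculations are unaffected.

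A reader might infer that the study will in fact report no eccentric hypertrophy, or that some known fraction of participants will be misclassified. Neither follows. The empty class results from applying Table 2 literally, and Section 8 offers a usable rule that the analysts may well have followed. The documents say nothing about how the variable was derived in practice, and they give no distribution of relative wall thickness.

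**What to change.** In Table 2, in both Section 9 and Section 10, replace the parenthesis after LVH with the Section 8 rule, for example: *LVH type: concentric if relative wall thickness >0.41, eccentric if ≤0.41*. The two copies should be changed together so that they stay identical.

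The cost is one phrase in two places. No measurement, sample size or analysis method changes.
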